273 This will be a 12-week randomized, double-blind, placebo-controlled interventional study
274 in 40 patients with T2DM and CAD with an acceptable glycemic control on their current
275 diabetes regimen who require elective coronary artery bypass grafting (CABG) regardless
276 of their participation in the study.

277 A minimum time frame of 3-week treatment will be considered to detect significant
278 changes in the study endpoints. If not all subjects would be able to complete the 12
279 weeks, study outcomes will be evaluated at the 3 week time point.

280

281 **Study Design** Study subjects will be randomized in two groups of 20 patients to receive
282 additional liraglutide, (L-group) or to remain on current treatment or placebo (D-group).

- 283 • L-group will be started on liraglutide. Liraglutide will be started and administered
284 for 12 weeks prior to CABG with a starting dose of 0.6 mg (after a least one week)
285 and subsequent increments to 1.2 mg (after a least one week) and to 1.8 mg (after
286 at least a week on 1.2 mg). The dose of 1.8 mg daily will be maintained until the
287 end of the 12-week study. Other and current diabetes treatment will be continued.
288 In those study participants who may be impacted by CABG scheduling and
289 COVID-19, and cannot complete the 12-week treatment, we will consider a
290 minimum time frame of 3 weeks to detect significant changes in the study primary
291 endpoints.
- 292 • D-group: placebo will be administered in addition to current treatment prior to the
293 CABG with a starting dose of 0.6 mg (after a least one week) and subsequent
294 increments to 1.2 mg (after a least one week) and to 1.8 mg (after at least a week
295 on 1.2 mg). Patients will be started on a supervised diet to achieve approximately
296 5% of weight loss between 3 and 12 weeks. In those study participants who may be
297 impacted by CABG scheduling and COVID-19, and cannot complete the 12-week
298 treatment, we will consider a minimum time frame of 3 weeks to detect significant
299 changes in the study primary endpoints.

300

301 Ultrasonographic measurement of EAT thickness will be performed at baseline and
302 after 12 weeks in all patients, regardless of the study arm.

303 All groups will receive lifestyle and diabetes education, and supervised diet as
304 part of the standard care, to insure similar glycemic control between arms and
305 weight loss. Study patient will be also required to check and log their finger stick

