419 baseline and before cardiac surgery that will be scheduled 12 weeks after study enrollment
420 and treatment. Adipose tissue collection will be collected during the cardiac surgery.
421 Study outcomes will be collected at 3 weeks in both groups in those patient who may not
422 be able to complete the 12- week treatment due to CABG logistics and COVID-19 impact
423 on scheduling

424

425 **Assessments for Efficacy**

426 **Adipose tissue collection:** EAT biopsy samples (average 0.5-1.0 g) will be taken, before
427 heparin administration, near the proximal tract of the right coronary artery. Each tissue
428 sample will be snap frozen in liquid nitrogen and stored at -80 °C until analysis in a freezer.
429 The subcutaneous fat tissue (SAT) will be harvested at the site of the thoracic wound and
430 preserved in the same manner.

431 **Gene expression:** in freshly isolated mature adipocytes (from EAT and SAT), extraction
432 of total RNA, quantification of mRNA, c-DNA generation qRT-PCR will be performed for
433 measuring expression of the inflammatory genes (TNF- α , IL-6) and GLP-1R.

434 **Western Blot:** Total proteins will be extracted from frozen EAT and SAT adipocytes and
435 blotted for TNF- α , IL6, as previously described.

436 In addition to the mRNA expression of GLP1R, we will also measure protein expression
437 of GLP-1R by western blotting. Total cell lysates from the EAT will be obtained as follows.
438 Cells will be resuspended in M-PER (Mammalian Protein Extraction Reagent, Thermo
439 Scientific), incubated on ice for 20 min, sonicated for a few seconds and then centrifuged
440 (14,000 rpm, 15 min, 4°C) to obtain protein lysates which will be stored at -80°C until
441 use. Protein content will be determined by Bradford assay before western blotting runs.
442 Antibodies will be anti-GLP1R Mab 3F52 (Novo Nordisk) and anti-GAPDH (GeneTex)
443 as loading control.

444 **Immunofluorescence**

445 To confirm GLP-1R protein expression, immunofluorescence will be performed on EAT
446 and SAT samples using Mab 3f52 against GLP-1R, as previously described by Pyke et al
447 23-24. This mouse monoclonal antibody has been extensively validated to show its
448 specificity. Due to the relatively low abundance of GLP-1R the immunofluorescence will
449 be performed using a tyramide signal amplification reagent (TSA kit#26 from Molecular
450 probes) according to the manufacturer instructions. In summary, cryosection of the samples

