572 **Subject Compliance**

573 We estimate that the majority of the participants who will be considered eligible will
574 complete the study. Attrition can be estimated as lower than 10%. In the event that
575 participants are lost to follow-up, the research coordinator will contact with the study
576 participant by telephone. The research coordinator will be trained in effective telephone
577 technique to maximize recruitment success. All groups will receive lifestyle and diabetes
578 education, as part of the standard care, to insure similar glycemic control between arms.
579 Study patients will be advised to monitor their capillary glucose twice daily, fasting in the
580 morning and post-prandially. Glucose profile will be tracked bi-weekly by the research
581 coordinator by email or telephone.

582

583 **Statistical Considerations**

584 POWER ANALYSIS

585 The statistical power (two-sided, $\alpha=0.05$) of the study was calculated to detect statistically
586 and clinically meaningful differences in the primary endpoint between the two study arms.
587 Our preliminary data showed that EAT inflammatory genes, including IL-6 and TNF- α are
588 upregulated in subjects with T2DM and CAD and higher in EAT as compared to SAT⁴⁻¹⁷.
589 From our recently published study, we calculated the average coefficient of variance (CV)
590 for differential inflammatory genes to be 42%, but for only 5 T2DM patients.¹⁷ As there
591 are no data on the effects of liraglutide on EAT inflammation, the power analysis was based
592 on our previous data and on the assumption that the difference in EAT TNF- α and IL-6
593 expression between liraglutide treated and placebo treated patients would be clinically
594 meaningful at 33% (approx. 1.3X fold). Based on these data, we propose to sample 40
595 individuals. There will be 20 on liraglutide plus standard therapy versus 20 subjects on
596 liraglutide-matching placebo plus standard therapy contributing EAT and SAT samples
597 collected during cardiac surgery. Using the power set at 90% and $\alpha=0.05$, and given the
598 CV of 42%, this sample size will provide adequate power to detect the clinically significant
599 expected difference (33%) in EAT TNF- α and IL-6 between the two study arms.

600 Based on pre-existing data, this sample size will provide adequate power to detect
601 statistically significant differences in EAT TNF- α and IL-6 between the two study arms in

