602 those patients who will receive treatment only for 3 weeks. The difference in EAT TNF- α
603 and IL-6 between liraglutide treated and placebo treated patients is expected to be
604 approximately 1X fold after 3 weeks of treatment.

605

606 The larger sample proposed in this current project would likely reduce the variability. To
607 further assure consistency of results, mRNA and protein expression values will be log-

608 transformed prior to statistical analyses unless they will be normally distributed.
 609 Housekeeping genes will be also used for both RT-PCR and western blot analyses.
 610 In those patients who will not complete the 12-week treatment, the analysis of EAT genes
 611 from the samples will be time adjusted

612
 613 Statistical power was also calculated to detect statistically significant differences in the
 614 ultrasound measured EAT thickness, secondary endpoint, between the two study arms Our
 615 group very recently showed that additional therapy with liraglutide for 12 weeks caused a
 616 reduction in ultrasound measured EAT from 9.6 ± 2 to 6.2 ± 1.5 mm ($p < 0.001$) in 54 patients
 617 with T2DM ¹¹. Given the reference value and the expected difference in EAT, the
 618 statistical power of the study (two-sided, $\alpha = 0.05$) was calculated.

619

Outcome	Reference value \pm SD	Expected Difference	Detectable difference with 80% power $\alpha = 0.05$	Detectable difference with >99% power $\alpha = 0.05$
EAT (mm)	9.6 ± 2	-20-or -30%	-20% (absolute difference = 1.9)	-30% (absolute difference = 2.88)

620

621 Assuming a difference of approximately 2 mm (20%) in EAT to be clinically significant
 622 (based on our recent and previously published data ¹⁰⁻¹⁴), a convenience sample of 20
 623 individuals for each group will therefore provide at least the statistical power (80%) to
 624 detect an expected difference of at least -20% in the EAT before and after treatment with
 625 liraglutide. Baseline standard Deviation (SDs) of 2 is expected to lower to approximately
 626 1.5 for the expected change. The expected change of SD will further assure significant
 627 statistical power of the comparative test.

628

629 In those study patients who will not be able to complete the 12-week treatment, we
 630 anticipate to see a 15% of EAT reduction after 3 weeks in patients who will be allocated to
 631 liraglutide. This anticipated 15% of EAT reduction will remain clinically significant. For

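### The claim of adequate power for TNF-alpha and IL-6 in patients treated only 3 weeks is unsupported: their number is not given and the stated 3-week effect cannot be interpreted

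*Combined protocol and SAP*

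**What the plan says.** Under Statistical Considerations (Power Analysis), the trial is sized at 20 per arm with two-sided alpha 0.05 and power set at 90%. The difference between arms is taken as "meaningful at 33% (approx. 1.3X fold). Based on these data, we propose to sample 40" individuals. The variability is "CV of 42%, this sample size will provide adequate power to detect the clinically significant" expected difference. The CV comes from 5 patients, and the same section says that no data exist on liraglutide and epicardial fat inflammation.

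The next paragraph extends the claim: "Based on pre-existing data, this sample size will provide adequate power to detect" differences in the two cytokines in "those patients who will receive treatment only for 3 weeks". The expected difference there is "approximately 1X fold after 3 weeks of treatment". No number of 3-week patients, 3-week variance or power figure follows.

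On timing, Study Type says that if not all subjects can complete 12 weeks, "weeks, study outcomes will be evaluated at the 3 week time point". Visit Procedures (Study Timetable) likewise has outcomes collected at 3 weeks in those who cannot complete. The primary endpoint under Endpoints, however, accepts treatment of at least 3 and up to 12 weeks. Tissue is obtained only at the operation: "and treatment. Adipose tissue collection will be collected during the cardiac surgery". The rationale for the 3-week minimum says that treatment length is set by the date of standard-care surgery.

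**The concern.** A power statement for a subset needs the size of the subset and an effect. Here neither is usable. The sample size quoted is that of the whole trial, while the patients described may be any fraction of it.

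A null result in short-treated patients would be read against a written assurance of adequate power. If the subset is small, such a null would say little about whether 3 weeks of treatment works.

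The fallback rule raises a related question. Taken literally, it moves the primary evaluation to week 3 as soon as one patient falls short of 12 weeks. It is then unclear whether the primary result rests on a 3-week subset or on everyone with tissue.

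**Working it through.** **Inputs.** All are from Statistical Considerations: 20 per arm, two-sided alpha 0.05, difference 33% (about 1.3X), CV 42%, t-test or Mann-Whitney test, log transformation unless the values are normally distributed. Subset sizes of 15, 10, 7 and 5 per arm are assumptions.

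**Method.** Two-sample t-test with n per arm: noncentrality = d × √(n/2), df = 2n − 2, power from the noncentral t distribution.

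**Standardised effects.**
- Raw scale: d = 33/42 = 0.786.
- Log-scale SD = √ln(1 + 0.42²) = 0.403.
- Ratio 1.3: ln(1.3)/0.403 = 0.651.
- Ratio 1.33: ln(1.33)/0.403 = 0.708.
- Ratio 0.67: −ln(0.67)/0.403 = 0.994.
- Doubling: raw 100/42 = 2.381; log ln(2)/0.403 = 1.720.

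**The plan's own figure.** At n = 20 on the raw scale, noncentrality = 0.786 × √10 = 2.485, the critical t (38 df) is 2.024, and power is 68% (70% by the normal approximation). The stated 90% is not reproduced; on this scale it needs 36 per arm. A one-sample formula with n = 20 gives 91.5%, but the planned comparison is between arms.

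**The 3-week effect as written.**
- As a ratio of 1, following the protocol's equation of 33% with about 1.3X, there is no difference and power equals alpha, 5%.
- As a doubling, the change is 100%, about three times the 33% of the main calculation.

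| Per arm | Doubling, raw | Doubling, log |
|---|---|---|
| 20 | >99% | >99% |
| 10 | 99.9% | 95% |
| 7 | 98% | 84% |
| 5 | 91% | 67% |

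**The main effect borrowed, granted in full at 3 weeks.**

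| Per arm | Raw, 33% | Ratio 1.3 | Ratio 1.33 | Ratio 0.67 |
|---|---|---|---|---|
| 20 | 68% | 52% | 59% | 87% |
| 15 | 55% | 41% | 47% | 75% |
| 10 | 38% | 28% | 32% | 56% |
| 5 | 20% | 15% | 17% | 28% |

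Granting the full effect is generous. In Study Design each dose step lasts at least a week, and 1.8 mg is reached only after "at least a week on 1.2 mg). The dose of 1.8 mg daily will be maintained until the" end of the study. So at least 7 + 7 = 14 of 21 days are below 1.8 mg. Nothing is deducted for attrition or for testing two cytokines.

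**Detectable difference.** This needs no assumed effect. On the raw scale, 80% power requires d of 0.909, 1.060, 1.325 and 2.024 at 20, 15, 10 and 5 per arm. Multiplied by 42%, these are differences of 38%, 45%, 56% and 85% of the mean, against the 33% called clinically meaningful.

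**The 3-week evaluation rule.** Each patient gives one epicardial sample, at surgery, on a date fixed by standard care. A patient operated on at week 7 or week 12 therefore has no week-3 tissue, so a literal week-3 evaluation of the primary endpoint is not possible for that patient. The Endpoints section would count the same patient's sample.

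**The case against.** The strongest reply is that 33% is not the protocol's 3-week input. The authors expect a difference and claim power to detect it, so they are unlikely to have meant a ratio of 1. If they meant a doubling, the adequacy statement is true on both scales down to about 7 per arm. This stands. A reader might infer that the plan's own inputs give 68% for 3-week patients, or that power is below 90% whatever the case. The documents do not support either inference, because both depend on borrowing the main effect. The doubling reading also lacks support: nothing in the protocol justifies a 3-week effect three times the main assumption.

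Second, Innovation argues that the effect may not depend on time. That is a reason to pool all durations. It does not supply the size of a subset.

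Third, a separate 3-week test may not be planned. The analysis text names no duration subgroup, says samples from non-completers will be time adjusted, and the endpoint spans 3 to 12 weeks. The Study Type sentence may only mean that 3 weeks is the minimum accepted. This is a fair reading, but the sentence does not say it and the time adjustment is not defined. A reader might also infer that the analysis set will be chosen after seeing the data. The documents leave room for that but do not show it.

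Fourth, the ratio of 0.67 should not be dismissed: the hypothesis is lower expression on liraglutide, and 1.3X may be loose wording. It is therefore kept in the range.

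Finally, the shortfall with all 20 per arm belongs to the main power calculation. What is particular here is the use of a whole-trial sample size for a subset of unknown size.

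**Conclusion.** The statement is wrong as written: it asserts adequate power without the inputs that power requires. Across the possible readings of the 3-week effect, power at 20 per arm runs from 5% to above 99%. With the main calculation's 33% and 42% CV it is 68% (52% to 87% by scale and ratio), and at any fixed non-zero effect it falls as the subset shrinks. These conditional figures rest on the full effect at 3 weeks, a CV from 5 patients and assumed subset sizes. They do not demonstrate that 3-week patients are underpowered, only that adequacy has not been shown.

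Read literally, the week-3 evaluation rule cannot be carried out for the primary endpoint and conflicts with the 3-to-12-week definition. Confidence is high on the missing inputs and on this conflict. It is lower on the actual power, which the documents do not allow anyone to fix.

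**What to change.** 1. Delete the adequate-power statement for 3-week patients. Alternatively, restate it as conditional on a named effect, with the figures above, and say that the number of such patients is unknown.
2. Replace the Study Type sentence on week-3 evaluation, and its counterpart in the Study Timetable, with: the primary comparison includes every randomised patient with epicardial fat collected at surgery, in the arm assigned, whatever the treatment duration or dose reached. This agrees with the endpoint as defined.
3. Report any results by duration as exploratory, with patient numbers and confidence intervals. If the time-adjusted analysis is kept, define it and treat it the same way.

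These are text changes with no extra patients, visits or assays. The downside is that the trial can make no confirmatory claim for 3-week treatment alone, and its stated power becomes less favourable.

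### The stated 90% power for EAT TNF-α and IL-6 does not follow from the plan's own inputs, and the weak 42% CV behind it is defended only by an incorrect statement about variability

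*Combined protocol and SAP*

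**What the plan says.** All of this is in Statistical Considerations, under the power analysis. The test level is two-sided 0.05 ("The statistical power (two-sided, $\alpha=0.05$) of the study was calculated to detect statistically"). The variability input is introduced with "From our recently published study, we calculated the average coefficient of variance (CV" and continues "for differential inflammatory genes to be 42%, but for only 5 T2DM patients", so the plan itself discloses the small source. The target is a between-arm difference described as "meaningful at 33% (approx. 1.3X fold). Based on these data, we propose to sample 40", with 20 patients per arm ("individuals. There will be 20 on liraglutide plus standard therapy versus 20 subjects on"). The conclusion is worded "Using the power set at 90% and $\alpha=0.05$, and given the" and then "CV of 42%, this sample size will provide adequate power to detect the clinically significant".

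Shortly afterwards, before the remarks on log transformation, comes the reassurance: "The larger sample proposed in this current project would likely reduce the variability".

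The section gives no formula, no CV for TNF-α or IL-6 separately, no CV for protein, and no power at any other CV. It says values will be log-transformed unless normally distributed, so the scale of the power calculation is open. Under Endpoints, the primary endpoint covers both mRNA and protein of the two genes.

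**The concern.** Two things look wrong. First, a standardised difference of 0.33/0.42 ≈ 0.79 with 20 per arm is well short of what 90% power needs in a two-arm comparison. Second, the plan recognises that its CV comes from 5 patients but does not show what happens if the CV is larger. Instead it says the variability will probably fall because more patients are enrolled. If variability means the spread between patients, that is incorrect: more patients estimate the spread better but do not make it smaller.

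The interpretation of the result is at stake. If the report repeats that the trial was adequately powered at 90%, a null finding on the primary endpoint would be read as evidence against an effect of the assumed size. The design may in fact have had a substantial chance of missing it.

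**Working it through.** **Inputs, all from the power analysis:** two-sided α = 0.05; n = 20 per arm; CV = 42%; difference 33%, also described as about 1.3-fold. For losses, Subject Compliance expects attrition below 10% and Subject Replacement rules out replacement. Losing 10% of 20 leaves 18 per arm.

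**Formula.** Two-sample t-test with 2n − 2 degrees of freedom and noncentrality δ / (SD × √(2/n)). With n = 20, √(2/n) = 0.3162 and the critical t on 38 df is 2.024. On the log scale, SD = √ln(1 + CV²) = √ln(1.1764) = 0.403.

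**Attempt to reproduce the 90% at CV 42%:**

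| Reading | δ | SD | Noncentrality | Power, 20 per arm | Power, 18 per arm |
|---|---|---|---|---|---|
| Raw scale, 33% of the mean, same SD in both arms | 0.33 | 0.42 | 2.48 | 67.8% | 62.9% |
| Raw scale, 33% reduction, CV 42% in each arm | 0.33 | 0.357 | 2.92 | 81.2% | 76.7% |
| Log scale, 1.3-fold | ln 1.3 = 0.262 | 0.403 | 2.06 | 51.9% | 47.5% |
| Log scale, 1.33-fold | ln 1.33 = 0.285 | 0.403 | 2.24 | 58.7% | 54.1% |
| Log scale, 33% reduction | −ln 0.67 = 0.400 | 0.403 | 3.14 | 86.5% | 82.5% |

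In the second row the SD is 0.42 × √((1 + 0.67²)/2). The last row is the most favourable, but a ratio of 0.67 is 1/0.67 = 1.49-fold, which conflicts with the plan's own description of about 1.3-fold.

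The normal approximation raises the first row to 70.0% and the last to 88.1%; neither is 90%. A one-sample t formula with 0.33/0.42 does give n = 20 (power 91.5%), but that is not the two-arm comparison the plan describes. By t-test, 90% at CV 42% would need 36 per arm in the first row and 23 in the last.

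**Sensitivity to the CV (t-test, 20 per arm):**

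| CV | 33%, raw scale | 33% reduction, log scale |
|---|---|---|
| 42% | 68% | 86.5% |
| 50% | 53% | 74% |
| 65% | 35% | 55% |

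Reaching 90% requires a CV of about 31% or less on the raw scale and about 39% or less on the log scale. Both are below the plan's own 42%.

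**How firm is a CV from 5 patients?** As an illustration for one gene under normality, an SD on 4 df has 95% limits SD × √(4/χ²). These are 0.42 × √(4/11.14) = 25% and 0.42 × √(4/0.484) = 121%. The one-sided 80% upper limit is 0.42 × √(4/1.649) = 65%. The plan's 42% is an average over several genes, so its precision differs and cannot be worked out from the documents.

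**The reassurance sentence.** The sample size enters the formula only through √(2/n). Going from 5 patients to 20 per arm reduces the standard error through that term. The SD is a property of the patients and the assay, and enrolling more of them does not lower it.

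**The case against.** The strongest reply is that the sentence about variability does no work in the calculation. The plan computes power at a CV of 42%, and no reduced CV enters the primary-endpoint figure. That is right. A reader might infer that the 90% rests on this sentence, or that the sample size was counted twice; the documents do not support either. Deleting the sentence changes no number. Its fault is that it stands where a sensitivity range should be.

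A reader might also infer that the 42% measures the wrong quantity, or that choosing differential genes biased it low. Neither is shown. A between-patient CV of EAT gene expression is the right kind of input for comparing surgical samples between arms. The Preliminary Data section cites the same source study for IL-6 and TNF-α, so both may be in the average. The selection rule and the gene list are not given, so the direction and size of any selection effect cannot be established.

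The range of 3 to 12 weeks of treatment could add spread, but the plan says analyses of early finishers will be time-adjusted, and its Innovation section argues that the effect may not depend on time. No size can be put on this from the documents.

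The plan also deserves credit for disclosing the 5-patient source. None of these replies restores the 90%.

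**Conclusion.** The concern holds in this form: 90% power is not delivered by 20 per arm, a 33% difference and a CV of 42% on any two-sided, two-arm t-test reading tried. The shortfall runs from about 3.5 percentage points (86.5%) on the most favourable reading, through 22 points (68%) on the plain one, to 31 to 38 points (59% to 52%) if the stated fold change is taken on the log scale. With 18 per arm, the plain and most favourable readings fall to about 63% and 82.5%.

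The 42% is imprecise, averaged, not specific to TNF-α or IL-6 and not shown for protein, so the true power could lie well to either side of these figures. The sentence offered in reply is incorrect if it refers to between-patient variability. The figures assume approximate normality on the stated scale and equal arms. The log-scale rows also assume that the CV converts as for a log-normal variable.

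**What to change.** Rewrite the primary-endpoint power paragraphs, with no change in enrolment:

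- Delete the sentence saying the larger sample will reduce variability.
- State the analysis scale and the formula, and reconcile 33% with about 1.3-fold, giving the direction of the change.
- Replace the averaged 42% with the CVs of TNF-α and IL-6 from the group's own 5-patient data, with upper confidence limits where available. Say whether any CV exists for protein.
- Replace the 90% with power over a range of CVs on the stated scale. For 33% on the raw scale: about 68% at CV 42%, 53% at 50% and 35% at 65%. For a 33% reduction on the log scale: about 86.5%, 74% and 55%. If 1.3-fold is kept as the target on the log scale, the figure at CV 42% is about 52%.
- Report the observed pooled CV with the results, so that a null finding can be judged against the precision achieved.

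The cost is a few lines of text and a less favourable stated power. The source CV was calculated from the group's own study, so no new data collection is needed for the mRNA figures.
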